# Blinding:

Treatments will be provided in an open-label manner. However, the analytical laboratory will remain blinded to treatment during the analysis of the plasma samples.

### 5.4 Subject Withdrawal and Replacement

A subject may withdraw from the study at any time at his or her own request or may be

This document is confidential.

Version: Draft 0.2, 21-Sep-2021

Controlled Document ID: 2805A.00, Effective Date 29-Jul-2019

Filing requirements: TMF Page 13 of 37

GSK Consumer Healthcare

withdrawn at any time at the discretion of the investigator or sponsor for safety, behavioral reasons, or the inability of the subject to comply with the protocol required schedule of study visits or procedures.

The following circumstances require discontinuation of study product and/or premature subject withdrawal:

- Protocol violation that may impact the subject's safety
- Positive test for COVID-19, conducted during the study, at times deemed necessary by Investigator
- Protocol violation that may interfere with the drug's PK profile, including
  - Any reported or suspected noncompliance of the smoking restriction during post dose PK observation period, e.g., CO > 10 ppm at any time during the 36 post dose period
  - Patch falls off or patch is inadvertently removed by the subject or those removed due to subject decision to discontinue from the study
- Withdrawal of informed consent
- Subject lost to follow-up
- Pregnancy

Version: Draft 0.2, 21-Sep-2021

Controlled Document ID: 2805A.00, Effective Date 29-Jul-2019

#### Analysis Sets

Subjects who deviate from the protocol will be identified and excluded from the pharmacokinetic analyses as agreed by the biostatistician and medical director or designee. Exclusion of any data from the analyses will be determined during a Blind Data Review (BDR) meeting prior to database lock. Any reasons for exclusion from an analysis population will be listed, if applicable.

The analysis of safety and tolerability parameters will be based on the Safety Population detailed in Section 6.1. The analysis of PK parameters will be based on the PK Population detailed in Section 6.2.

#### 6.1 Safety Population

The Safety Population is defined as all randomized subjects who receive at least one dose of study medication.

### 6.2 Pharmacokinetic Population

The PK population is defined as all randomized subjects who completed both periods, and who had no major protocol deviations concerning pharmacokinetics regardless of patch adhesion score.

The following PK analysis set is defined to address the PK objective and further PK considerations within this study:

 PK analysis set includes all subject of the PK population, for which the relevant predoseadjusted PK parameters (at least one AUC or Cmax) can be derived. This analysis set will be used in PK summaries, the primary analysis, and the secondary analysis.

### General Aspects for Statistical Analysis

#### 7.1 General Methods

SAS® for Windows, Release 9.4 (SAS® Institute Inc., Cary, NC, USA) software will be used to perform all data analyses.

All data in the database will be presented in the data listings. Unless otherwise stated, all listings will be sorted by subject number and assessment date/time, when applicable.

The following labels for treatment will be used on all tabulations where the results are displayed by treatment, in the following order:

- NicoDerm CQ Dungarvan (Test)
- NicoDerm CQ Alza (Reference)

#### 7.2 Summary Statistics

Unless otherwise stated, continuous variables will be summarized using the number of observations (n), and the statistics arithmetic mean, standard deviation (SD), geometric mean,

This document is confidential.

Version: Draft 0.2, 21-Sep-2021

Controlled Document ID: 2805A.00, Effective Date 29-Jul-2019

Filing requirements: TMF Page 15 of 37

GSK Consumer Healthcare

coefficient of variation (CV%), median, minimum, and maximum. The minimum and maximum values will be presented to the same number of decimal places as recorded in the CRF, arithmetic mean and median will be presented to one more decimal place than the raw data and the SD will be presented to two more decimal places than the raw data. Categorical variables will be summarized with frequency counts and percentages. Percentages will be rounded to one decimal place, with the denominator being the number of subjects in the relevant population, unless otherwise stated.

For the plasma PK data, the data will be rounded to two decimal places in the listings, except for the following situations:

- λz data: rounded off to four decimal digits.
- Pharmacokinetic parameters related to time such as Tmax, Kel Lower, and Kel Upper must be reported with the same precision as the actual sampling time: rounded off to 3 decimal digits.
- Concentration versus time data, as well as Cmax: reported to 4 decimals.

Summary statistics including the geometric mean (three decimal places) and coefficient of variation (CV) (%) (one decimal place).

Only data from nominal protocol scheduled visits will be included in the summary tables. Data from unscheduled visits will not be included in the summary tables but will be included in the listings and figures.

All assessments will be presented in the listings.

### 7.3 Key Definitions

#### Study Day:

Study day will be calculated using first patch administration (either Test or Reference) date as the reference date. If the date of interest occurs on or after the first patch administration date, study day will be calculated as (date of interest – first patch administration date) + 1. If the date of interest occurs prior to the first patch administration date, study day will be calculated as (date of interest – first patch administration date). There will be no study day 0.

#### Prior medication:

Medication/treatments taken within 90 days of signing the informed consent form will be documented as a prior medication/treatment.

#### Concomitant medication:

Medications/treatments taken after the first patch administration will be documented as concomitant medication/treatments.

Treatment: Treatment is assigned as the last received treatment, except in the case of pre-dose measurements. Any non-adverse event assessment occurring on the same calendar date as a given patch application before dosing would be attributed to the same treatment given on that

This document is confidential.

Version: Draft 0.2, 21-Sep-2021

Controlled Document ID: 2805A.00, Effective Date 29-Jul-2019

Filing requirements: TMF Page 16 of 37

GSK Consumer Healthcare

calendar day. If no patch was applied on the same calendar day then any measurements predose will not be summarized by treatment. Adverse events will be summarized only by the last received treatment.

Age:

Defend as age at Study day 1 = (Study day 1) visit date - date of birth + 1) / 365.25 and truncated to complete years.

Height:

Height (in cm) = height (in inches) \*2.54

Weight:

Weight (in kg) = weight (in lbs) \* 0.4536

BMI:

BMI  $(kg/m^2)$  = Weight $(kg)/[Height(m)^2]$ 

### 7.4 Handling of Dropouts and Missing Data

All data from subjects who withdraw from the study will be included in the summaries up to the time of withdrawal.

For safety,

- If an AE is recorded with an onset date corresponding to a patch application day, but the time is missing, then the AE will be assigned to the actual treatment with patch application that day and considered treatment-emergent.
- If an AE is recorded with an onset date that does not correspond to a patch application
  day, but the time is missing, then the AE will be assigned to actual treatment that
  covers the AE onset day and considered treatment-emergent if appropriate.
- If an AE is recorded with an onset date where day and time are both missing, then the
  AE allocation to a treatment will be done on a case by case basis considering
  available information (e.g. AE onset date, AE end date, AE comments, subject
  disposition) in raw data. It will be considered treatment-emergent if appropriate.
- Missing data are represented on subject listings as either a hyphen ("-") with a
  corresponding footnote ("- = unknown or not evaluated"), or as "N/A", with the
  footnote "N/A = not applicable", whichever is appropriate
- Dates that are missing because they are not applicable for the subject are output as "N/A", unless otherwise specified.

For PK analysis, only observed concentration data will be used in the data analysis except for concentration values BLQ as described in Section 9.1 and Section 9.2. No attempt will be made to extrapolate or interpolate estimates for missing data.

This document is confidential.

Version: Draft 0.2, 21-Sep-2021

Controlled Document ID: 2805A.00, Effective Date 29-Jul-2019

Filing requirements: TMF Page 17 of 37

GSK Consumer Healthcare

### 8. Demographic, Other Baseline Characteristics and Medication

#### 8.1 Inclusion and Exclusion Criteria

All recorded inclusion/exclusion criteria status will be presented in a data listing for the Safety Population. Each subject's inclusion or exclusion from each population will also be presented in a data listing.

### 8.2 Demographics and Body Measurements

The demographic characteristics will consist of age (years), sex (female or male), ethnicity (Hispanic or Latino, Not Hispanic or Latino, Not Reported, and Unknown), race (American Indian or Alaska Native, Asian, Black or African American, Native Hawaiian or Other Pacific Islander, White, Chinese, Multiple, Australian Aborigine/Torres Strait Islander, and Other). The body measurements consist of height (cm), weight (kg), and body mass index (BMI) (kg/m^2).

Descriptive statistics (n, mean, SD, Min, median, and Max) will be calculated for body measurements using the last results obtained prior to first patch administration. Frequency counts and percentages will be tabulated for categorical variables. All demographic characteristics will be summarized by treatment group and listed by subject for the Safety Population and PK Population. If the Safety Population and PK Population are the same, the table for the PK Population will not be generated.

### 8.3 Medical History

Medical history will be listed by subject. Any abnormal findings from the physical exam occurring before the first patch administration will be included in the Medical History. The Medical Dictionary for Regulatory Activities (MedDRA®) Version 24.0 will be used to classify all medical history findings by System Organ Class (SOC) and Preferred Term (PT).

#### 8.4 Urine Illicit Drug Screen and /Alcohol breath test

A urine illicit drug screen will be performed at screening and Day -2 test for testing includes: cocaine, THC, opiates/opioid's, benzodiazepines, 3,4-methylenedioxy-N-methylamphetamine (MDMA)/ecstasy, methamphetamine and amphetamines.

An alcohol breath test will be performed at screening and Day -2.

The urine illicit drug screen and alcohol breath test and restriction assessments will be presented in a separate listing for the Safety Population.

### 8.5 Virology

Virus serology will be performed at screening for HBs Ag, anti-HBc (IgG + IgM), anti-HCV Ab, HIV 1 and HIV 2 antibodies. Findings from Virology results will be included in listings for the Safety Population.

This document is confidential.

Version: Draft 0.2, 21-Sep-2021

Controlled Document ID: 2805A.00, Effective Date 29-Jul-2019

Filing requirements: TMF Page 18 of 37

GSK Consumer Healthcare

# 8.6 Pregnancy Testing and Follicle Stimulating Hormone (FSH) Levels

For female subjects of childbearing potential, a serum pregnancy test, will be performed at screening and end of study (or early termination). A urine pregnancy test will be performed at day -2 and day 4. Pregnancy tests will also be done whenever one menstrual cycle is missed during the active study period (or when potential pregnancy is otherwise suspected). Pregnancy tests may also be repeated as per request of IRBs/ECs or if required by local regulations

FSH will be performed at the screening visit for females who have been amenorrhoeic for 1 year.

Results from the pregnancy testing and FSH Levels will be listed, separately, for the safety population.

### 8.7 COVID-19 Testing

Nasopharyngeal swab will be collected to test for COVID-19 using RT PCR or antigen test, at screening, Day -2, early discontinuation or end of study, and at any time during residential period in the study when subjects report symptoms suggestive of COVID-19. A listing including all results from COVID-19 testing will be created.

### 8.8 Electrocardiogram

A standard 12-lead ECG will be performed at screening. Results of any clinically significant abnormalities should be reported in the CRF. Clinically significant abnormalities should also be recorded on the Adverse Event CRF. All findings will be listed.

#### 8.9 Prior and Concomitant Medications

Concomitant medication use will be recorded from the time the subject signs the ICF until the EOS visit. Concomitant medication use is permitted if indicated by the investigator for premedication or treatment of an AE.

Concomitant medications will be coded using the World Health Organization Drug Dictionary (WHO DD), Version B3, Mar 2021 or later. For the purpose of inclusion in Prior and concomitant medication tables, incomplete medication start and stop dates on CRF will be imputed as follows:

- · If the stop date is incomplete, the following rules will be applied:
  - Missing day: Assume the last day of the month;
  - Missing day, month, and year: Assume that the medication is continuing;
  - In the case of the death of a subject, and if the imputed end date is after the date of death, the end date will be imputed as the date of death.
- If the stop date is incomplete, imputed end date will be used instead of reported end date
- If the start date is incomplete, the following rules will be applied:

This document is confidential.

Version: Draft 0.2, 21-Sep-2021

Controlled Document ID: 2805A.00, Effective Date 29-Jul-2019

Filing requirements: TMF Page 19 of 37

GSK Consumer Healthcare

- Missing day: Assume the first day of the month;
- However, if the partial date and the date of Patch administration lie within the same month
  and year and the date of Patch administration is not after the stop date of the medication, set
  to the date of Patch administration. Otherwise, set to stop date of the medication.
  - Missing day and month: Assume January 1st.
- However, if the partial date and the date of Patch administration lie within the same year and
  the date of Patch administration is not after the stop date of the medication, set to the date of
  Patch administration. Otherwise, set to stop date of the medication.
  - Missing day, month, and year: Assume date of Patch administration if it's not after the stop date for the medication. Otherwise, set to stop date for the medication.

For the missing day imputation, the following examples should be used for reference:

Example 1:

Medication start: UNJUN2019 Medication end: 20OCT2019

Date of administration: 16OCT2019

Medication start imputed: 01JUN2019

Example 2:

Medication start: UNOCT2019
Medication end: 20OCT2019

Date of administration: 16OCT2019

Medication start imputed: 16OCT2019

Example 3:

Medication start: UNOCT2019 Medication end: 20OCT2019

Date of administration: 24OCT2019

Medication start imputed: 20OCT2019

Relative start day or end day with respect to the dose date of the patch will not be calculated if the medication start date or end date is incomplete.

All prior and concomitant medications will be presented in data listings for the Safety Population.

#### 8.10 Study Drug Administration

The study drug administration details including date and time of administration, Treatment

This document is confidential.

Version: Draft 0.2, 21-Sep-2021

Controlled Document ID: 2805A.00, Effective Date 29-Jul-2019

Filing requirements: TMF Page 20 of 37

**GSK Consumer Healthcare** 

Description, and the question "Patch Application applied" (and reason if no) will be listed by Subject. An additional listing for Patch Removal time will also be included.

All patch adhesion summaries and analysis will be conducted on the Safety Population.

Adhesion will be assessed five times during each administration of the patches: within 5 minutes from patch application, at approximately 6, 12, and 18 hours after patch application, and immediately prior to patch removal.

Summary statistics will be derived for all subjects whose patch fell off (adhesion score of 4) and the patch wear time of all subjects, separately (arithmetic mean, SD, minimum, median and maximum).

A frequency table will be created showing the adhesion score for each patch per assessment timepoint.

### 8.11 Study Drug Compliance

The number of subjects exposed to each treatment will be tabulated for the safety population. Treatment deviations for individual subjects will be listed and summarized. Cases of partial exposure, and subjects with baseline > 5% of the  $C_{max}$  will also be summarized.

Version: Draft 0.2, 21-Sep-2021

Controlled Document ID: 2805A.00, Effective Date 29-Jul-2019

GSK Consumer Healthcare

#### 9. Pharmacokinetic Analyses

All plasma concentration and PK parameter summaries and analysis will be conducted on the PK Population. All concentration and PK data will be listed (Safety Population). This includes any data for subjects who are not included in the analysis (i.e. subjects withdrawn from the study due to adverse events). The listing for plasma concentration will include planned timepoint, sample collection (yes or no), date and times of collection, and the calculated time deviations from the planned timepoint.

#### 9.1 Correction for Non-Zero Baseline of Nicotine

For the primary analysis the following corrections will be performed:

When predose concentrations are greater than the lower limit of quantification (LLOQ), baseline-adjusted nicotine plasma concentrations will be used to determine the following pharmacokinetic parameters using standard noncompartmental techniques: maximum plasma concentration observed (Cmax), area under the plasma concentration versus time curve from time zero to the real time corresponding to the last concentration above LLOQ (AUC0-it) and the area under the plasma concentration versus time curve extrapolated to infinity (AUC0-inf).

The pre-dose nicotine concentration will be estimated using the using the  $\lambda_z$  calculated from the subjects own data as follows:

C(t) adjusted= C(t) observed-C (0)  $e^{-\lambda_z t}$ 

# 9.2 Handling of Concentrations Below the Lower Limit of Quantification (BLOQ), No Reportable Concentration Values, and Missing Data

For the analysis of all individual plasma concentrations and all secondary PK parameter, all concentration BLOQ values that occur before Cmax will be treated as zero (0). BLOQ values after Cmax will be treated as "Not Detectable" (ND), which will be shown as missing for plasma PK concentrations and PK parameter estimation.

Samples with invalid concentration (due to bioanalytical or clinical issue) will be replaced by "0.00" when it occurs prior to patch application. Otherwise they will be set to missing for tabulation, graphical representation and calculation purposes if it occurs after patch application.

If any concentration data is missing or deviates from the planned time of collection, then the pharmacokineticist may calculate the PK parameters using the available data.

Missing values of  $\lambda_z$  can be estimated from the subject's  $\lambda_z$  value from the other treatment. If a  $\lambda_z$  value cannot be calculated from the other treatment, then the  $\lambda_z$  will be obtained from the treatment mean value for subjects with non-missing values of  $\lambda_z$  in the period in which it is not available. This estimated  $\lambda_z$  can be used to calculate other  $\lambda_z$  dependent variables. This  $\lambda_z$  value derivation is only applied for pre-dose concentration adjustments.

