### 12.3.8 Handling of Dropouts and Missing Data

All existing data for subjects who are dropouts from the study will be included in the pharmacokinetic statistical analysis.

If any concentration data is missing or deviates from the planned time of collection, then the pharmacokineticist may calculate the PK parameters using the available data.

Missing values of  $\lambda_z$  can be estimated from the subject's mean  $\lambda_z$  value from the other treatments. If a  $\lambda_z$  value cannot be calculated from the other treatments, then the  $\lambda_z$  will be obtained from the treatment mean value for subjects with non-missing values of  $\lambda_z$  in the period in which it is not available. This estimated  $\lambda_z$  can be used to calculate other  $\lambda_z$  dependent variables. This  $\lambda_z$  value derivation is only applied for pre-dose concentration adjustments.

For nicotine concentration:

- BLOQ values obtained before  $C_{max}$  will be imputed as zero.
- BLOQ values obtained after  $C_{max}$  will be "Not detectable" (ND), which will be shown as missing (explanations will be specified in the footnote of TFLs).

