#### 9.5 Plasma Pharmacokinetic Parameters

Plasma concentrations from nicotine will be used to calculate the following parameters by standard non-compartmental methods for Part A, B, and C (Day 1):

PK Parameter	Definition		
	Primary PK Parameters		
AUC 0-t	Area under the plasma concentration versus time curve from time zero to time t, where t is the time of the last measurable plasma concentration of nicotine, estimated, computed using the linear trapezoidal rule		
AUC 0-inf	Area under the plasma concentration versus time curve calculated from time zero to infinity. $AUC_{0-inf} = AUC_{0-t} + C(t)/\lambda_z$ where $C(t)$ is the concentration at the last measurable sampling time point and $\lambda_z$ is the terminal elimination rate constant)		
C max	The highest observed plasma nicotine concentration		
Secondary PK Parameters			
t max	Time to maximum plasma nicotine concentration		
t½	Apparent elimination half-life, calculated as ln(2)/λz		
$\lambda_z$	Apparent elimination rate constant for plasma nicotine computed as the slope		

This document is confidential.

Version: Draft 0.2, 21-Sep-2021

Controlled Document ID: 2805A.00, Effective Date 29-Jul-2019

GSK Consumer Healthcare

PK Parameter	Definition
	of the regression line of ln (C(t)) on time.

-The linear trapezoidal method will be employed for all incremental trapezoids arising from increasing concentrations and the logarithmic trapezoidal method will be used for those arising from decreasing concentrations.

- \(\lambda\)z will be estimated at terminal phase by linear regression after log-transformation of the concentrations.
- -Only those data points that are judged to describe the terminal log-linear decline will be used in the period after regression.

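### A below-LLOQ value between two measurable concentrations is set to zero before Cmax but to missing after it, so AUC handling depends on where Cmax falls (low priority, cheap to fix)

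*SAP*

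**What the plan says.** Protocol 12.3.8 (Handling of Dropouts and Missing Data) has two rules for nicotine concentrations. Those headed "BLOQ values obtained before" Cmax "will be imputed as zero". Those after Cmax are labelled not detectable and shown as missing. The rule is not limited to particular parameters.

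SAP 9.2 makes the same split at Cmax: "all concentration BLOQ values that occur before C max will be treated as zero (0". That sentence opens with a scope, "For the analysis of all individual plasma concentrations and all secondary PK parameter", which does not name the primary parameters AUC0-t, AUC0-inf and Cmax. SAP 7.4 says of PK analysis in general that "only observed concentration data will be used in the data analysis except for concentration values BLQ as described in" SAP 9.1 and 9.2. SAP 11 declares no change from the protocol.

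SAP 9.2 also has a separate rule for samples whose concentration is invalid for a bioanalytical or clinical reason. Before application they become zero. "Otherwise they will be set to missing for tabulation, graphical representation and calculation purposes if it occurs after patch application". It does not say whether an isolated BLOQ result counts as invalid.

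Cmax is the highest observed concentration (protocol 12.3.1, SAP 9.5), and the patch is worn for 24 h.

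**The concern.** Zero is a sensible value for a BLOQ result before drug has appeared in plasma. The rule does not stop there; it runs to Cmax. With a 24 h patch, Cmax may fall anywhere on a long plateau. If it is at 24 h, 14 post-dose samples (0.5 to 20 h) precede it, and 13 of them (1 to 20 h) can lie between two measurable post-dose concentrations.

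Take a BLOQ result at 12 h with measurable values at 10 and 14 h. If the highest sample was at 10 h, the result is missing and the trapezoid bridges 10 to 14 h. If the highest was at 16 h, the same result is a true zero. Spurious or real, it deserves the same treatment in both cases. The position of the maximum can also differ between a subject's two periods.

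At stake are AUC0-t and AUC0-inf, two of the three parameters that decide bioequivalence. A spurious zero lowers that profile's AUC and adds within-subject noise. Cmax is not affected, because a BLOQ value is never the maximum.

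**Working it through.** **Plan's own figure.** The documents give no figure for the effect of BLOQ handling. The one design figure that can be reproduced is enrolment: 12 / (1 − 0.40) = 20, as stated in protocol 12.1 and SAP 5.2. The 12 is used below.

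**Inputs from the documents.** Sampling at predose, 0.5, 1, 2, 3, 4, 5, 6, 8, 10, 12, 14, 16, 18, 20, 24, 25, 26, 27, 28, 30, 32 and 36 h (SAP 9.4); 24 h wear; half-life 1 to 4 h (protocol 4.2); linear trapezoidal rule (protocol 12.3.1); intra-subject CV 13%; 12 evaluable subjects; limits 0.80 to 1.25.

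**Inputs assumed.** No LLOQ, concentration level or tmax is given. The calculation therefore uses 27 one-compartment profiles: patch release constant or declining with a half-life of 24 or 12 h; a skin-absorption step with half-life 0.5, 1 or 2 h; elimination half-life 1, 2 or 4 h.

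**Mechanism.** Under the linear rule, a zero at sample i removes C_i × (t_{i+1} − t_{i−1}) / 2 from AUC. The time weight comes from the schedule alone. On a flat 24 h plateau:
- 1 h weight (3 to 5 h samples): 1/24 = 4%
- 2 h weight (8 to 18 h samples): 2/24 = 8%
- 3 h weight (20 h sample, neighbours 18 and 24 h): 3/24 = 12.5%

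**Profiles.** Each sample before Cmax was in turn set to zero. Loss of AUC0-t across the profiles:

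| Sample | Loss from one zero |
|---|---|
| 0.5 h | 0.02 to 0.3% |
| 1 h | 0.1 to 1.4% |
| 2 h | 0.4 to 4.1% |
| 3 h | 0.7 to 5.4% |
| 4 to 5 h | 1.1 to 6.0% |
| 6 h | 2.8 to 8.0% |
| 8 h | 5.0 to 9.5% |
| 10 to 18 h | 6.0 to 9.0% |
| 20 h | 12.4 to 12.6% |

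The 0.5 h row is the lag case: no post-dose sample precedes it, so zero stays appropriate. The 20 h row arises only with Cmax at 24 h. With Cmax at 5 to 10 h, the largest possible loss is about 5 to 9.5%.

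Set to missing instead, for samples from 2 h on, the absolute error is 0.08% at the median and 0.48% at most. This takes the true concentration to lie on the curve, that is, the BLOQ to be spurious.

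**Effect on the trial.** Take the worst case, one 20 h zero in one of 12 subjects:
- Shift in log ratio: ln(0.875) / 12 = −0.1335 / 12 = −0.0111, so the ratio moves by −1.1%. Losses of 2% and 8% move it by 0.2% and 0.7%.
- Variance of the within-subject log difference: 2 × ln(1 + 0.13²) = 0.0335. Adding 0.1335² / 12 = 0.0015 gives 0.0350.
- Interval width: √(0.0350 / 0.0335) = 1.02, about 2% wider.
- With an observed ratio of 1.00 (assumed) and t = 1.812 on 10 df, the 90% interval is exp(±1.812 × √(0.0335/12)) = 0.909 to 1.101. With the zero it becomes exp(−0.0111 ± 1.812 × √(0.0350/12)) = 0.897 to 1.091. Both lie well inside 0.80 to 1.25.

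**The case against.** **The invalid-sample rule already handles it.** If an embedded BLOQ is an assay or sampling anomaly, SAP 9.2 already sends invalid post-application samples to missing, and a Blind Data Review before lock decides exclusions. This is the strongest reply, and it shows that the proposed treatment fits the plan. It does not close the gap: a BLOQ result from a valid assay run is a reportable result, and nothing in the SAP classes it as invalid. Two rules in one section could then give opposite answers for one sample. In an open-label study, where only the laboratory is stated to be blinded, that choice should be fixed in advance.

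**The SAP rule does not name AUC.** This stands in part. A reader might infer that SAP 9.2 on its face puts zeros into the primary AUC; its opening words do not say so, and SAP 7.4 only refers back to it. The firm route is protocol 12.3.8, which has no such limit and from which SAP 11 declares no departure. On the narrow reading, the SAP simply has no BLOQ rule for its primary parameters.

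**The value may be real.** If delivery truly fell, zero is nearer the truth and bridging overstates AUC. This stands, and the fix allows for it.

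**The log trapezoid fails at zero.** SAP 9.5 says "the logarithmic trapezoidal method will be used for those arising from decreasing concentrations", and ln(C/0) is undefined with no fallback stated. A reader might infer a serious computational fault. With a linear fallback, the linear and linear-up/log-down rules agree within 0.1 percentage point, so this needs only a clarifying word.

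**Conclusion.** The point holds as a low-priority improvement. The rule is stated, not merely incomplete, and it can give a wrong AUC for a profile with a spurious BLOQ value on the established curve: under 1.5% at 1 h, 0.4 to 6% at 2 to 5 h, about 3 to 9.5% at 6 to 18 h, and 12.5% at 20 h with Cmax at 24 h, against under 0.5% if bridged. These sizes rest on assumed profiles and on the BLOQ being spurious.

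Two stronger readings are not supported. A reader might infer that the bioequivalence conclusion is at risk. The documents give no evidence that plateau BLOQ values will occur; they should be rare, and one moves the ratio by at most about 1.1% with 12 subjects. A late Cmax would make more samples subject to the zero rule, but says nothing about how often a BLOQ occurs. A reader might also infer bias towards one product. The rule is the same for both, and which product is hit would be chance.

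**What to change.** In SAP 9.2, state for primary and secondary parameters alike:

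- BLOQ values before the first measurable post-dose concentration are set to zero.
- A BLOQ value between two measurable post-dose concentrations, before or after Cmax, is flagged in the listing, queried with the laboratory and set to missing for parameter estimation, in line with the existing invalid-sample rule.
- BLOQ values after the last measurable concentration are not used.
- If any embedded value occurs, the AUC comparison is repeated with that value as zero and reported as a sensitivity result.

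Declare this in SAP 11 as a change from protocol 12.3.8.

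The cost is a few sentences and no new data. Handling would no longer depend on the position of Cmax, the question of scope would be settled, and no imputed zero could follow a measurable value in the main AUC calculation. The downside is some overstatement of AUC if delivery truly fell, for example with recorded patch lift; the sensitivity result, read with the adhesion scores, covers that case.
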